3.2 Derived variables

Results based on derived variables will be sense-checked by the chief investigator. In addition, the code will be checked by the senior statistician.

3.3 Procedures for missing data

The primary effectiveness analysis will be based upon those randomised participants who provide at least one of the three post-treatment assessments of physical function contributing to the primary outcome.

The five QLQ-C30 items contributing to the physical function scale are as follows:

1. Do you have any trouble doing strenuous activities, like carrying a heavy shopping bag or a suitcase?
2. Do you have any trouble taking a long walk?
3. Do you have any trouble taking a short walk outside of the house?

4. Do you need to stay in bed or a chair during the day?
5. Do you need help with eating, dressing, washing yourself or using the toilet?

A patient will be considered to have completed the physical function scale and to have a score of zero (lowest level of physical functioning), if their reason for not having a physical function score is recorded as due to being in intensive care or having died prior to the questionnaire being due. This is a reasonable assumption about responses to the above five questions in those circumstances and is to prevent these values being implicitly imputed by the statistical model upon which the analysis is based. This approach will only be used for the physical function and role function scales, where the assumption of a zero value can be justified; the number of values imputed in this way will be reported by treatment group. The two items contributing to role function are:

6. Were you limited in doing either your work or other daily activities?
7. Were you limited in pursuing your hobbies or other leisure time activities?

Participants missing their baseline assessment of a patient reported outcome will be included in the analysis by (i) imputing the overall mean for the corresponding observed baseline measurements, (ii) including an indicator variable as a covariate with values 0 if the individual has provided a baseline measure, and value 1 if not. This approach has been shown to give unbiased estimates in a randomised trial, and to avoid the loss of power that a complete case analysis will cause(8).

When single items are missing from any of the patient reported outcomes, these will be addressed using the accepted guidelines where available.

3.4 Study centre effects

Variation between centres will be accommodated in each analysis by including dummy variables, distinguishing each centre (Bristol and Bath, plus Salford and South Manchester will be combined) in the regression model. There is no plan to investigate variation in the treatment effect by study centre.

3.5 Visit windows

Late completion of assessments may prove unavoidable in a small number of cases, but for the data to be accepted the assessments must be completed:

Pre-surgery:	before the day of surgery
Post-surgery:	
3 days:	no earlier than day 2 and no later than day 4
6 days:	no earlier than day 5 and no later than day 9

3 weeks:	no earlier than day 10 and no later than day 34
6 weeks:	no earlier than day 35 and no later than day 66
Post-randomisation:	
3 months:	no earlier than day 67 post-surgery, and no later than day 111
6 months:	no earlier than 5 months and no later than 7 months
9 months:	no earlier than 8 months and no later than 10 months
12 months:	no earlier than 11 months and no later than 14 months
18 months:	no earlier than 15 months and no later than 20 months
24 months:	no earlier than 21 months and no later than 30 months

Wide windows for completion have been allowed, so that all data obtained from the longer-term follow-up can be used. However, efforts will be made to encourage completion within 10 days of each assessment point. Variation in the timing of completion will be accommodated by the statistical analyses. As the data from the feasibility study are now contributing to the primary analysis, these time windows will be applied to feasibility and main studies – this is a slight change to the windows in the feasibility study protocol.

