2.8 Blinding

In the first week post-surgery patients will be blinded using large adhesive dressings, positioned similarly on all trial patients regardless of the type of surgery (covering abdominal, thoracic, and cervical incisions). The first dressing should be applied by the surgical team in the operating theatre. The dressing will not be changed unless required; it will then be changed according to local practice. If dressings are changed, the patient will be asked to turn their head away from the wound sites to prevent them from observing the wounds. The nurse will clean the sites of all actual and potential incisions. Dressings will be removed as per local practice at one-week post-surgery. The surgical team will not be blind to allocation.

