2.10.2 Secondary outcomes

Secondary outcomes will assess the efficacy of the two approaches (morbidity and safety) and establish oncological markers of quality assurance of surgery which are surrogate markers of long-term survival (detailed histopathology and quality assurance of the radicality of surgery). Secondary outcomes will include:

1. All-cause short and long-term complications
2. Impact of complications up to hospital discharge will be categorised using the Clavien-Dindo System(2).
3. Spirometry measures of forced expiratory volume in one second (FEV₁) and forced vital capacity (FVC)
4. Success of blinding during the first six days post-surgery, using the Bang Blinding Index(3).
5. Generic and disease specific HRQL measures EORTC QLQ-C30(4), and QLQ-OES18(5), multidimensional fatigue inventory (MFI-20)(6), EuroQoL EQ-5D-5L(7) from which we will calculate quality adjusted life years (QALYs).
6. Quality assurance of surgery with histopathological and surgical measures
7. Overall and recurrence-free survival to two years
8. Length of hospital stay, defined as length of primary hospital stage plus readmission within 30 days (and length of primary hospital stay plus length of hospital stay if discharged to community hospital)
9. Further measures of NHS resource use and costs.

The assessment points are pre-surgery, post-surgery at three days, six days, three weeks, and six weeks, and post-randomisation at three, six, nine, twelve, eighteen and 24 months.

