6.4.5 Post-operative pain

Using the full analysis set, the number responding, median, first and third quartile pain scores will be presented for LAO and OO groups at each of three days and six days. Medians and first and third quartiles will be presented. The null hypothesis of no true difference in pain at 6 days, comparing LAO and OO groups will be tested using the Mann-Whitney U test. Where patients have responded with a score between 0 and 10 rather than completing the visual analogue scale, the score will be converted by assuming that each point score = 10mm along the visual analogue scale.

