6.6 Sensitivity analysis

If, at one or more of the three time points contributing to the primary outcome, more than 20% of data is missing, the recorded reasons for missing data will be assessed, and data at the three time points imputed in accordance with those reasons. This imputed dataset will be the basis of a sensitivity analysis.

As participants whose surgery could not be completed are likely to be informed of this, the analysis of pain at six days post-surgery will be repeated using the per protocol set.

The primary outcome requires that the average time from randomisation to surgery is the same for the study groups being compared. We will conduct a sensitivity analysis, additionally adjusted for each patient's time from randomisation to surgery.

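### The six-day window runs to day 9, past dressing removal at one week, so the six-day pain test can include scores from patients who have seen their wounds

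*SAP*

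**What the plan says.** - **Blinding (SAP 2.8).** "In the first week post-surgery patients will be blinded using large adhesive dressings". The period then ends: "Dressings will be removed as per local practice at one-week post-surgery".
- **Window (SAP 3.5).** The section lists when, "for the data to be accepted the assessments must be completed". For the six-day assessment this is "no earlier than day 5 and no later than day 9". No narrower window is given for pain or for the blinding question.
- **Pain test (SAP 6.4.5).** "The null hypothesis of no true difference in pain at 6 days, comparing LAO and OO groups will be tested" by a Mann-Whitney U test in the full analysis set.
- **Repeat of that test (SAP 6.6).** Because patients whose surgery could not be completed will probably be told so, "the analysis of pain at six days post-surgery will be repeated using the per protocol set".
- **Blinding check.** The outcome list (SAP 2.10.2) has "Success of blinding during the first six days post-surgery, using the Bang Blinding Index". SAP 6.7 describes the same index as covering the first week. SAP 3.1 places analyses of blinding in the per protocol set.

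**The concern.** The reason given in 6.6 for repeating the pain analysis shows that the plan treats patients' knowledge of their surgery as a threat to this comparison. It deals with one route to that knowledge, surgery that was not completed. The window in 3.5 opens a second route. A patient who had the allocated surgery and answers on day 8 or 9 may already have seen the wounds, and stays in both the main test and the per protocol repeat.

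If patients expect less pain after LAO, that expectation can enter late scores. The share of late forms might also differ between arms. For the Bang index, guesses made after the wounds are visible would make blinding look worse than it was while the dressings were on.

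**Working it through.** The SAP states no figure on this point that could be reproduced, so the check compares dates and analysis rules.

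**1. Dates.** Accepted days for the six-day assessment (3.5): 5, 6, 7, 8, 9, which is five days. Scheduled dressing removal (2.8): one week, taken as day 7.

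- Days after removal: 8 and 9, so 2 of 5.
- If removal comes before the form is completed on day 7: 7, 8 and 9, so 3 of 5.

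These are counts of calendar days, not of patients. The SAP does not give the distribution of completion days.

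**2. Does any analysis rule deal with late forms?**

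- SAP 3.5 says in general terms that the analyses will allow for variation in completion time. Neither the Mann-Whitney test in 6.4.5 nor the Bang index in 6.7 has a term for completion day.
- The repeat in 6.6 selects on whether the allocated surgery was completed, not on completion date or dressing status.
- SAP 3.5 encourages completion within 10 days of each assessment point. For the six-day form that is looser than the window itself.

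**3. Does the mismatch reach the Bang index?** The SAP does not say on which form or day the guess is collected. The listed post-surgery assessment points within the first six days are three days and six days (2.10.2), so collection on the six-day form is a reasonable inference, but only that.

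**4. Illustration for the index, on assumptions that are not in the SAP.** Let *q* be the share of an arm's guesses given after removal, *b* the index among those patients, and 0 the index among blinded patients. Then

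observed index = *q* × *b* + (1 − *q*) × 0 = *q* × *b*

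| *q* | *b* = 1 (all guess correctly) | *b* = 0.5 |
|---|---|---|
| 5% | 0.05 | 0.025 |
| 10% | 0.10 | 0.05 |
| 20% | 0.20 | 0.10 |
| 30% | 0.30 | 0.15 |

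The column *b* = 1 is an upper limit: SAP 2.5.2 allows LAO patients an abdominal incision of under 8 cm for a feeding jejunostomy, so seeing the wound need not settle the guess. The SAP supports no particular value of *q*. No bias in the pain test can be calculated from the document.

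**The case against.** Several points limit the concern, and most of them stand.

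- **A blinded pain comparison is already planned.** Table 4 marks three-day pain with the footnote for a Mann-Whitney p-value, and its window (days 2 to 4) lies wholly within the dressing period. A reader might infer that the trial has no cleanly blinded pain comparison; the document does not support that. Nor is pain the only patient-reported outcome at six days: the supplementary tables also list QLQ-C30 scales there.
- **The Bang index is bounded by its own stated period.** A guess on day 8 or 9 lies outside both the first six days and the first week. A reader might infer that the plan definitely admits such guesses. It does not say so; it only fails to exclude them.
- **Late forms may be rare.** The nominal day is 6, and 3.5 expects late completion in few cases. That is an expectation and not a control, but it makes large late shares hard to assume.
- **Restricting the main test would have its own cost.** Completion before removal is a post-randomisation event. If sicker patients answer later and this differs by arm, dropping their forms would introduce selection into a comparison set in the full analysis set. This argues against changing the main analysis, but not against a sensitivity analysis.

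What remains is that the dates do not fit together for the six-day pain test, and no section resolves it.

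**Conclusion.** The point holds in a limited form. The accepted window for the six-day assessment extends two days, possibly three, past the scheduled end of patient blinding, and neither the planned pain test nor its per protocol repeat identifies or removes the affected scores. For pain this follows directly from 2.8, 3.5, 6.4.5 and 6.6. For the Bang index it depends on the guess being collected on the six-day form, which is inferred. In addition, 2.10.2 and 6.7 give different periods for the index.

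The reach is one secondary outcome and the blinding check. The primary outcome is measured from three weeks onward, after the dressings are off by design, and is unaffected. It would be going too far to say that the six-day comparison is biased or that the index will report failed blinding: the number of late forms is unknown, and so is the effect of seeing the wounds on the scores. This is a cheap improvement to the plan, not a flaw in its main conclusions.

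**What to change.** - **6.4.5:** keep the six-day pain test in the full analysis set as the main analysis.
- **6.6:** add a sensitivity analysis of six-day pain limited to forms completed before dressing removal. Use the recorded removal date. If it was not recorded, use forms completed by day 7, with a day 6 variant.
- **Reporting:** give the number of six-day forms completed after removal, by arm.
- **6.7:** compute the Bang index only from guesses given before dressing removal, and state on which form and day the guess is collected.
- **2.10.2 and 6.7:** reconcile the two stated periods for the index.

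The cost is a few lines of SAP text, one further analysis, and slightly fewer observations in the restricted analysis and in the index. The acceptance window can stay as it is, and dressing practice is not changed.

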4. DESCRIPTION OF PARTICIPANT CHARACTERISTICS

4.1 Disposition

The flow of patients through the trial will be summarised in a CONSORT diagram that will include the eligibility, reasons for exclusion, numbers randomised to the two treatment groups, those undergoing their allocated surgery, losses to follow up and the numbers analysed (see Figure 1 in Section 8 of this plan).

4.2 Baseline characteristics

Summary statistics for patient characteristics, as determined at baseline, will be presented separately for those subsequently allocated to LAO and OO. The patient characteristics presented will allow the ROMIO patients to be compared to cohorts in other studies of oesophagectomy (see Table 1 in Section 8 of this plan).

5. ASSESSMENT OF STUDY QUALITY

5.1 Eligibility checks

The numbers of patients and reasons for exclusion will be described; this information will be presented in the CONSORT flow chart.

5.2 Participating surgeons

The number of surgeons participating at each centre, and confirmation that they met the entry criteria for participation in ROMIO, will be presented in the text of the main reports.

5.3 Study completion

All patients will be followed up for 24 months post-randomisation, for vital status, and through completion of PROs. If possible within the study follow-up period, patients can be followed up for 36 months.

5.4 Compliance

The number of patients who, post-randomisation, opt for surgery other than that allocated, will be reported in the CONSORT flow chart.

5.5 Fidelity to allocated surgery

Surgeons are completing check-lists for, and photographing key aspects of each procedure, to assess whether they are abiding by the listed mandatory and prohibited actions for OO, and for LAO. The number of procedures for which fidelity was maintained will be reported by study arm for patients in the per protocol set, and the nature of the deviation presented by study group for other patients.

Conversions from allocated surgery to another approach, and cases where the allocated surgery could not be completed, will be reported in the CONSORT flow chart (these patients are not part of the per protocol set) and reasons noted in the text.

5.6 Changes made to the statistical analysis plan

Subsequent versions of the statistical analysis plan will include a table of changes made since the previous version. When the plan cannot be followed in the primary effectiveness analysis, infringements of the plan will be detailed with reasons in the report of primary results.

6. ANALYSIS OF EFFECTIVENESS

6.1 Patients found to be ineligible post-randomisation

For patients found to be ineligible post-randomisation, the reason for ineligibility will be noted, and the patient invited to continue in follow-up. Where the required data are provided, the patient will be included in the full analysis set for the intention to treat analysis of effectiveness.

6.2 Summary of primary and secondary outcomes

For patients in the full analysis set, the number of patients providing data, mean, and standard deviation will be presented, by allocated group, for the time points used in the analysis of the primary outcome: baseline, three and six-weeks post-surgery, and three months post-randomisation. The primary outcome is based on the physical function scale of the QLQ-C30, a continuous measure with high scores indicating better physical function.

With regards to secondary outcomes, the same statistics will be presented for other scales derived from patient reported outcomes:

For function scales derived from the QLQ C-30 (role, emotional, cognitive, social), and global health status, high scores indicate high functioning / good quality of life.

For symptom scales derived from the QLQ C-30 (fatigue, nausea and vomiting, pain, dyspnoea, insomnia, appetite loss, constipation, diarrhoea, financial difficulties), high scores indicate greater symptom burden.

For the function scale derived from the QLQ-OES18 (dysphagia), a high score indicates good functioning.

For the symptom scales and items derived from the QLQ-OES18 (eating, reflux, pain, trouble swallowing saliva, choked when swallowing, dry mouth, trouble with taste, trouble with coughing, trouble talking), a high score indicates a high symptom burden.

For the five scales derived from the MFI-20 (general fatigue, physical fatigue, reduced activity, reduced motivation, mental fatigue) a high score indicates greater fatigue.

For the full analysis set, the occurrence of deaths, and of disease recurrence over a two-year follow-up period will each be presented for the LAO and OO groups as a Kaplan-Meier survival curves. Point estimates from these survival curves will be presented at 30 days and 90 days to allow comparison with National Audit Data.

For the safety set, the occurrence for each patient of one or more complications in each of the following key categories, both up to hospital discharge, and separately for the remainder of the 24-month follow-up, will be tabulated for the LAO and OO groups: oesophagoenteric leak and conduit necrosis/failure (patients experiencing each and both of these will be reported), chyle leak, pneumonia, gastrointestinal bleeding requiring intervention or transfusion. The number of patients requiring readmission to ITU/HDU will also be presented.

For the per protocol set, summary statistics for the histopathological and surgical measures of quality will be presented for each of the LAO and OO groups, including length of oesophagus, total count of malignant ‘positive’ nodes, total count of all nodes, carcinoma positive circumferential resection margins, carcinoma positive proximal and distal resection margins, and pT stage.

6.3 Primary analysis

The null hypothesis being addressed by the primary analysis is that, in truth, physical functioning in the three months following randomisation, measured with the physical function scale of the QLQ-C30, is identical whether access for a patient’s oesophagectomy was achieved with LAO or OO.

Using the full analysis set, the following analysis will be conducted separately for feasibility and full trial patients:

The relative effectiveness of the two approaches will be quantified as a difference in mean response on the physical function scale of the QLQ-C30 (LAO mean – OO mean), amongst patients in the full analysis set, using patients’ available measures from the three-week and six-week post-surgery, and the three-month post-randomisation assessments. The difference in mean response will be presented with its 95% confidence interval, and p-value.

The difference in means will be estimated in a mixed effects linear regression model with patient response at three-week (y_{i1}) and six-week (y_{i2}) post-surgery, and three-month (y_{i3}) post-randomisation as the outcome variables (i.e. between one and three outcome measurements per patient), and covariates: treatment allocation ($x_{1i}=1$: LAO; $x_{1i}=0$: OO), baseline physical function (x_{2i}), dummy variables distinguishing centres ($x_{3ki}=0,1$; $k=1,\dots,K$ indexing the centres), two dummy variables distinguishing assessment points ($x_{4ti}=0,1$; $t=1,2,3$), and a dummy variable distinguishing patients who underwent neoadjuvant treatment or not ($x_{5i}=1$: underwent neoadjuvant treatment; $x_{5i}=0$: no neoadjuvant treatment). Finally a dummy variable distinguishing those participant without a baseline assessment of outcome ($x_{6i}=1$: no baseline assessment; $x_{6i}=0$: baseline assessment available). A normally distributed random effect will accommodate the correlation between each patient’s responses: $z_i \sim N(0, \sigma_z)$. A normal distribution is assumed for the residual errors: $e_i \sim N(0, \sigma_e)$. The coefficient for the treatment allocation covariate (β_1) is the intention to treat estimate of treatment effectiveness, comparing LAO to OO. In statistical notation:

$$y_{it} = \beta_0 + \beta_1 x_{1i} + \beta_2 x_{2i} + \sum_{k=1}^K \beta_{3k} x_{3ki} + \sum_{t=1}^3 \beta_{4t} x_{4ti} + \beta_5 x_{5i} + \beta_6 x_{6i} + z_i + e_i$$

The estimates from the feasibility and full trial patients will both be presented, with a third pooled estimate computed as a mean of the feasibility and full trial estimates, weighted by the inverse of the variance of the estimate (equivalent to a fixed-effects meta-analysis).

This pooled estimate is the primary estimate of relative treatment effectiveness.

6.4 Secondary analyses

6.4.1 Patient reported outcome questionnaires

Using the full analysis set, the primary analysis plan will be adapted to the analysis of each of the other scales from patient reported outcomes. For these secondary analyses, it may be necessary to present the pooled estimate (combining feasibility and full trial estimates) in the paper, with the feasibility and full trial specific estimates presented in supplementary material. Where the feasibility and full trial estimates are noticeably different to the extent of supporting different conclusions, this will be highlighted.

